Sample size: 35 patients (15 from St Mary's Hospital Imperial College Healthcare NHS Trust, London, UK recruitment center and 20 from Virginia Mason Medical center, Seattle, USA). Sample size has been determined pragmatically based on the predicted number of patients undergoing treatment for esophageal cancer in recruitment centers during the study period. It is noted that even in high volume centers such as Virginia Mason Medical Center and St Mary's Hospital the longitudinal accrual of patients at the time of diagnosis and definitive surgery seldom exceeds 20-30 patients per year. Accordingly number of patients decided from each site during the intended 8 month study period is a conservative estimate of study recruitment. It is intended that data obtained from this pilot study will support formal power calculations for future studies.

Aspects of recruitment, consenting, data collection, and data storage will be the responsibility of each of the recruiting center. Separate ethical approval for this study will be sought at both Virginia Mason Medical Center and St Mary's Hospital where the conduct of the research will be required to meet local standards. Responsibility for the conduct of research at each site will be assigned to the local lead ([name] at Virginia Mason Medical Center and Professor [name] at St Mary's Hospital).

Inclusion criteria:

Patients with the following characteristics will be eligible for inclusion in this study:

- i. aged 18-90 years
- ii. newly diagnosed (prior to treatment) with esophageal and/or gastroesophageal junctional cancer (adeno- or squamous cell carcinoma)
- iii. planning to undergo curative treatment, including surgical resection with neoadjuvant therapy

Exclusion criteria:

Patients with the following characteristics will not be eligible for inclusion in this study:

- i. pregnant females
- ii. without malignant esophageal disease
- iii. inability or unwillingness to provided informed written consent

Methodology: patients undergoing curative treatment for esophageal cancer will be recruited at the time of routine clinical assessment shortly following initial diagnosis

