and will undergo clinical evaluation at two study time points: (1) staging investigation (e.g. laparoscopy or endoscopy) and (2) definitive surgical resection. Study time points have been judiciously chosen to coincide with interventions that form part of patient's routine clinical care. It is intended that sampling will occur on the day of each intervention/surgery following a routine period of fasting.

Breath sample collection:

Analysis of breath acetone from samples collected from Virginia Mason Medical Center and St Mary's Hospital will be performed using a KETONIX® point of care device. Patients will be asked to exhale directly into this handheld device, which provides an on-line and real-time measurement of breath acetone concentration in parts per million.

At St Mary's Hospital breath acetone analysis will also be performed using the Proton Transfer Reaction Mass Spectrometry (PTR-MS) in order to provide cross platform validation of results.

Blood sampling:

At each study time point a single sample of venous blood (15ml) will be collected for the purpose of determining serum concentrations of a number of metabolic and inflammatory markers, e.g. C-reactive protein (CRP), albumin, lipid profile, glucose, insulin, acetone, insulin-like growth factor (IGF), macrophage inhibitory cytokine-1 (MIC-1), interleukin-1 (IL-1), interleukin-6 (IL-6), interleukin-10 (IL-10), and; tumor necrosis factor alpha (TNFa). Once collected, samples will be centrifuged and the supernatant (serum) will be aliquoted for storage at -80°C.

Analysis of serum CRP, albumin, lipid profile, glucose and insulin will be performed within the biochemical pathology laboratories of the individual recruitment centers. The remaining biochemical parameters will be analyzed using commercial available enzyme-linked immunosorbent assays (ELISA) kits. An agreement has been reached with the Benaroya Research Institute at Virginia Mason to conduct the ELISA analysis for all samples.

Indirect calorimetry:

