At the time of sample collection, patients will also undergo assessment of resting energy expenditure by indirect calorimetry (Fitmate, COSMED Inc, Chicago, USA). This non-invasive measurement is made by asking patients to exhale at rest into a sterile facemask that is placed over their mouth and nose. Subjects will be asked to exhale into this facemask at a normal rate and tidal volume for approximately 5 minutes while measurement of their resting energy expenditure is determined. Prior to taking measurements patients will be required to remain seated at rest for 20 minutes (in the majority of cases patients will have already been waiting for longer than this duration in department wherein they are undergoing either their surgery or other intervention). Patient will be assessed on the day of surgery or other intervention and hence will be

fasting as part of their routine care. Patients will be requested to abstain from smoking and exercise for four hours prior to testing. We will also record their food consumption in the preceding 3 days.

Assessment of body composition:

CT images that are routinely obtained at the time of diagnosis and following neoadjuvant therapy will be used to determine body composition parameters. Pseudonymized images at the anatomical level of the midpoint of the body of the third lumbar vertebra will be obtained and exported to a Digital Imaging and Communications in Medicine (DICOM) format. Images are pseudonymized at the time of retrieval from the hospital picture archiving and communication system (PACS, which removes all patient related information from the saved DICOM image. Images will be subject to segmentation to determine cross sectional muscle and adipose area using commercially available software (SlicOmatic Ver 5.0, Tomovision, Magog, Canada). Analysis of CT images will be performed at each recruiting institution. Definitions of skeletal muscle index, sarcopenia and visceral obesity have been previously (**APPENDIX IV**)(15, 16).

Data collection

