The following data will be retrieved from the patient's electronic medical record (EMR) for inclusion into the database: medical record number; date of birth; sex; ethnic origin; comorbidities; details of neoadjuvant and adjuvant therapy; details of pre-operative nutritional supplementation; pathological stage and tumor characteristics. Additional data capture at the time of sampling will include: height; weight; any recent antibiotics (≤ 4 weeks); time of last oral intake; three day dietary report (to be completed retrospectively on the day of sampling); health-related quality of life questionnaires (QLQ-OES18, QLQ-C30, QLQ-CAX24); Patient generated subjective global assessment (PG-SGA) food intake category; performance status (ECOG, determined by either [name] or [name]); GPS, and; patient reported weight loss in last 6 months at study time point 1. The CTCAE (17) and ECCG (18) definitions will be used when reporting outcomes of chemotherapy and surgery respectively.

Sample storage

Blood samples will be stored in a -80°C freezer within the Benaroya Research Institute. Samples will be labeled using a unique study identifier composed of the patient's study ID and the date the sample was collected.

Data storage

Virginia Mason Medical Center subject data will be stored in a pseudonymized form within a suitable platform (e.g Microsoft Office Excel or REDCap). Data will be stored on a password protected institutional (Virginia Mason Medical) computer. Paper records (including completed questionnaires) will be stored in locked filing cabinet with the department of Thoracic Surgery Virginia Mason Medical Center. Access to the data will

be limited to the principal investigator and nominated members of the research team only. Any data from samples shared with external collaborators in the United Kingdom or Canada will be in a linked anonymized form.

Data collected at St Mary's Hospital will be stored and protected as per local IRB requirements and sent to Virginia Mason Medical for inclusion in the data analysis via a secure system (e.g., Box).

Data analysis

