Univariable and linear regression analysis will be used to compare exhaled acetone concentrations with body composition parameters. The coefficient of variation will be determined for repeated measurements recorded using the Ketonix device. Acetone concentrations measures using the Ketonix device and PTR-MS (St Mary's Hospital only) will be compared using Bland Altman plots. Comparisons between continuous data will be made using either the Mann-Whitney U test or Student t test, whilst categorical variables will be compared by χ^2 or Fischer exact test. Statistical significance will be assigned to 2-sided P values <0.05 .

F. PROTECTION OF HUMAN SUBJECTS

Risks to human subjects:

Human Subject involvement and characteristics

Human subjects will be enrolled into this study. The purpose of recruiting human subjects is to determine the influence of esophageal cancer and neoadjuvant therapy on nutritional status and inflammatory markers. Recruitment of human subjects is critical to achieving the intended outcomes of this study.

Patients with newly diagnosed esophageal and/or gastroesophageal junctional cancer (adeno- or squamous cell carcinoma will be recruited from Virginia Mason Medical Center (n=20) and St Mary's Hospital (n=15). Patients will be asked to donate an exhaled breath sample and blood sample (15ml) at two study time points. Patients' resting energy expenditure will also be determined and patients will be asked to complete a three day dietary diary, PG-SGA food intake and quality of life questionnaires at each study time point. Any other data that are utilised as part of this study originates from patients' routine clinical care and EMR.

We do not plan to enroll vulnerable subject groups (children, persons with mental disability, prisoners) where ability to give voluntary informed consent maybe questioned or compromised.

Enrollment:

Collaborating sites:

This work will be conducted as part of a collaboration between Virginia Mason Medical Centre (Seattle, USA) and St Mary's Hospital (Imperial College Healthcare NHS Trust, London, UK).

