APPENDIX IV

Methodology for calculating specific parameters of body composition:

CT or positron emission tomography with computed tomography scan acquired as part of patient's routine care will be acquired. Images at the anatomical level of L3 or the L3-L4 intervertebral disc space will be obtained and exported to a Digital Imaging and Communications in Medicine (DICOM) format. Images will be subject to automatic segmentation to determine cross sectional muscle and adipose area. Definitions of skeletal muscle index, sarcopenia and visceral obesity are provided below (15, 16).

Figure IVA. Example of automatic skeletal muscle (central panel) and adipose tissue (right panel) segmentation

Skeletal muscle index (SMI) will be calculated as the ratio of lean tissue area to height:

$$SMI \text{ (cm}^2/\text{m}^2\text{)} = \frac{\text{Lean tissue area (cm}^2\text{)}}{\text{Height (cm}^2\text{)}}$$

Sarcopenia will initially be defined as SMI <52.4 cm²/m² for men and <38.5 cm²/m² for women (15). The following formulae will be used to determine lean body mass and fat mass:

$$\text{Lean body mass (Kg)} = 0.30 \times [\text{Lean tissue area (cm}^2\text{)}] + 6.06$$

$$\text{Fat mass (Kg)} = 0.042 \times [\text{Total fat area (cm}^2\text{)}] + 11.2$$

Visceral obesity is defined as a fat area >163.8 cm² for men and >80.1 cm² for women.

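### The acetone regressions on body composition name no sex term, although the protocol's own cut-offs treat the body-composition measures as strongly sex-dependent

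*Protocol*

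**What the plan says.** Section E, Data analysis, describes this analysis in one sentence: "Univariable and linear regression analysis will be used to compare exhaled acetone concentrations with body composition parameters". The variables are acetone concentrations and body-composition levels. No covariate or stratum is named. The test rule follows in the same paragraph: "Statistical significance will be assigned to 2-sided P values <0.05".

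The Data storage section has the St Mary's data "sent to Virginia Mason Medical for inclusion in the data analysis via a secure system", so the two hospitals (20 and 15 patients) are analysed together. Sex is on the list of data taken from the medical record.

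Appendix IV defines the body-composition measures by sex. After "Sarcopenia will initially be defined as SMI" it gives 52.4 cm²/m² for men and 38.5 for women, and it sets visceral obesity at a fat area of 163.8 cm² for men and 80.1 cm² for women.

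Correlating acetone with nutritional status, body composition included, is the first secondary outcome. The Sample size paragraph says the pilot data should support power calculations for later studies.

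**The concern.** A correlation computed over men and women together has two parts: the association within each sex, and the part that arises because the sexes differ on both variables. Only the first says whether acetone tracks body composition. The second appears whenever acetone differs by sex, even if acetone and muscle or fat are unrelated among men and among women. Its sign depends on the direction of the acetone difference, so it can imitate an association or hide one.

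At stake is the reading of a secondary outcome and the use of its estimate. In a pilot of 35 the point estimate matters more than the P value, because it is what a later sample-size calculation would take up.

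**Working it through.** **The plan's own figure.** The protocol gives no power and no target correlation for this study ("Sample size has been determined pragmatically based on the predicted number of patients"). Only the total can be reproduced: 20 + 15 = 35. The nearest prior correlations are in Appendix III, from an obesity cohort: rho −0.262 with BMI and −0.375 with percentage loss of excess body weight.

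**Inputs from the protocol.** n = 35; two-sided 0.05; SMI cut-off gap 52.4 − 38.5 = 13.9; fat-area cut-off gap 163.8 − 80.1 = 83.7.

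**Assumptions not in the protocol.** Share of men p = 0.70-0.85; mean sex gap equal to the cut-off gap; within-sex SD 7-10 for SMI and 60-100 cm² for visceral fat area; sex difference in acetone d_y from 0 to 0.8 within-sex SD. The standardised SMI gap is then d_x = 13.9/10 = 1.39 to 13.9/7 = 1.99. For fat area it is 83.7/100 = 0.84 to 83.7/60 = 1.40.

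**Formula.** With zero correlation within each sex, the pooled correlation is r = r_x × r_y, where each term is d√(p(1−p)) / √(1 + d²p(1−p)).

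**Worked case** (75% men, SMI SD 8, d_y = 0.5):
- √(0.75 × 0.25) = 0.433 and d_x = 13.9/8 = 1.74.
- r_x = 0.752/√1.566 = 0.601.
- r_y = 0.2165/√1.047 = 0.212.
- r = 0.601 × 0.212 = 0.127.

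**Range for SMI.** The low end is 85% men with SD 10, the high end 70% men with SD 7.

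| Sex difference in acetone | Induced \|r\| | Share of 0.262 | Share of 0.375 |
|---|---|---|---|
| 0 | 0 | 0 | 0 |
| 0.2 SD | 0.032-0.061 | 12-23% | 8-16% |
| 0.5 SD | 0.078-0.150 | 30-57% | 21-40% |
| 0.8 SD | 0.122-0.232 | 47-88% | 33-62% |

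For visceral fat area at 0.5 SD the range is 0.05-0.12.

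**False-positive rate at n = 35.** By Fisher z for the worked case: atanh(0.127) = 0.128; standard error 1/√32 = 0.177; ratio 0.72. The chance of passing ±1.96 is about 0.108 + 0.004 = 0.11, against 0.05 nominal. Simulation (20,000 runs) gave 11.5% for this case. Other simulated cases with 80% men (10,000 runs each) gave:
- 6.7% (d_x 1.5, d_y 0.3)
- 8.6% (d_x 1.5, d_y 0.5)
- 17.6% (d_x 1.74, d_y 0.8)

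In these 80%-men cases, with sex and site in the model, the rate was 4.8-5.1%.

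**Context.** At n = 35, |r| must exceed 0.334 for P < 0.05, and power is 33% for a true 0.262 and 61% for 0.375. Distortion of the estimate is therefore the larger issue.

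**Site, by the same formula** (p = 15/35, √(p(1−p)) = 0.495):
- 0.3 SD on both variables: (0.1485/√1.022)² = 0.02.
- 0.5 SD on both: (0.247/√1.061)² = 0.06.
- 0.8 SD on both: (0.396/√1.157)² = 0.14.
- A difference on one variable only: 0.

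**The case against.** **The wording does not rule out adjustment.** A reader might infer that the protocol commits to unadjusted analysis throughout. It does not. Listing linear regression beside univariable analysis may well mean a multivariable model, the Appendix III work moved from correlations to multivariable regression, and covariates are often left to an analysis plan that is not shown. This stands. But the univariable analysis is explicitly planned and is unadjusted by definition, and the predictors listed for the Appendix III model (neutrophil count, glucose, acetone, low-density lipoprotein) do not include sex.

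**No sex difference in acetone is documented.** This also stands. Without one the bias is zero. The cut-offs are not means, so their gap only stands in for a mean gap.

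**Levels or change.** The Significance paragraph of Section C speaks of how variation in acetone relates to changes in body composition. In an analysis of within-patient change, stable sex offsets would cancel. The Data analysis sentence, however, refers to concentrations and body-composition parameters.

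**Site.** A reader might infer that the hospitals differ in breath instruments and laboratories and so confound the regression equally. The protocol does not support this. Both use the Ketonix device; PTR-MS at St Mary's is an addition for cross-platform validation. The assays run "within the biochemical pathology laboratories of the individual recruitment centers" are CRP, albumin, lipids, glucose and insulin, none of them breath acetone or body composition. What remains is "Analysis of CT images will be performed at each recruiting institution", with the same named software. Reader differences alone affect one variable and induce no correlation.

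**The comparator.** A reader might take 0.262 as the correlation expected here. The protocol states none. That value and 0.375 come from an obesity cohort, a different mass-spectrometry platform, and BMI or excess-weight measures.

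**Conclusion.** The point holds as an improvement to the stated method, not as a demonstrated error. The protocol plans a pooled univariable analysis of measures that it treats as sex-dependent, and it names no sex term. If acetone differs by sex by about half a standard deviation, the induced correlation through SMI is 0.08-0.15, or 30-57% of the smaller preliminary correlation and 21-40% of the larger. In the worked case the false-positive rate is about 11% instead of 5%. At 0.2 SD the effect is small, and with no difference it vanishes. All of this rests on an assumed share of men, assumed SDs, and the cut-off gap standing in for the mean gap. The top of the range (0.23) needs every assumption at its extreme. The case for a site term is much weaker than the case for a sex term.

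**What to change.** State in the Data analysis section that regressions of exhaled acetone on body-composition parameters include sex as a covariate. Make the sex-adjusted partial correlation with its 95% CI the main estimate and report the univariable result beside it. Recruiting site may be added as a secondary covariate or a sensitivity analysis, because the CT images are read locally.

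No new data are needed. The cost is one degree of freedom for sex, or two with site, out of 35 − 2 = 33. For the correlation, the Fisher-z standard error rises from 1/√32 = 0.177 to 1/√31 = 0.180 with sex. A slope on SMI loses more, because the between-sex part of the SMI variance is no longer used. In the worked case that part is 0.601² = 36%, so the slope's standard error grows by up to 1/√0.64 = 1.25 times. With 70-85% men there would be only about 5 to 10 women (35 × 0.15 to 35 × 0.30), too few for a reliable separate estimate in women. A common adjusted estimate is therefore more practical than sex-specific ones.

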Principal Investigator
[name] [name] MD
[name] FACS FRCS (c) FRCSI (Hon) FRCSE (Hon)

Head of Thoracic Surgery and Thoracic Oncology
Director Digestive Disease Institute Esophageal Center of Excellence
President Ryan Hill Research Foundation
Virginia Mason Medical Center
[name]
[name]
[contact]

Study Title:
**Influence of NSarcoPenia on Esophageal
Cancer ouTcomes (INSPECT study)**

APPROVED
12/10/2019
BRI IRB

Table of Contents

A. SPECIFIC AIMS.....	3
B. BACKGROUND AND SIGNIFICANCE	5
C. PRELIMINARY STUDIES	7
D. RESEARCH DESIGN AND METHODS.....	9
E. PROTECTION OF HUMAN SUBJECTS	13
F. REFERENCES	22
G. CONSULTANTS	24
H. APPENDIX.....	25

A. SPECIFIC AIMS

Hypothesis: Esophageal cancer is associated with changes in patient's body composition that are correlated with biochemical markers of cell metabolism (acetone) and systemic inflammation. Knowledge of these changes can influence patients' care through modification of treatments and outcome prediction.

Purpose: An observational, pilot study to assess longitudinal variation in exhaled acetone, body composition and other markers of nutritional status and inflammation in patients undergoing multimodal therapy for esophageal cancer. Where possible variations in these markers will be correlated with changes to early and late treatment outcomes as well as nutritional interventions that form part of patients routine care.

B. STUDY OUTCOMES

Primary outcome

- i. Longitudinal assessment of breath acetone in patients undergoing multimodal therapy for esophageal cancer

Secondary outcomes

- i. Correlation of breath acetone with alternate measures of nutritional status including anthropometric measurements, body composition, resting energy expenditure and blood parameters
- ii. Correlation of breath acetone and alternate measures of nutritional status with patient reported nutritional intake and quality of life
- iii. Assessment of the repeatability and accuracy of point of care testing of breath acetone using the Ketonix device

C. BACKGROUND AND SIGNIFICANCE

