Patient recruitment has been divided equally between the two sites and each site will be responsible for local recruitment, consenting, and data collection. All biological samples will be analyzed at the local recruiting hospital, with the exception of the analysis of specific mediators (i.e. acetone, IL-1, IL-6, IL-10, TNF α , MIC-1, IGF) which will be conducted within the Benaroya Research Institute for samples collected from both study sites.

Sources of Materials:

Patients will be required to provide written informed consent prior to enrollment in this study. Participants will be provided with an approved informed consent form and will receive careful explanation by the investigator of what is involved by taking part in the study, including potential risks and benefits.

- i. Patient demographics and meta-data will be recorded for all patients (please see data collection section above). There is a small risk of breach of confidentiality.
- ii. Breath samples: breath sampling is entirely non-invasive and poses negligible risk of harm to patients. Patients will be asked to provide a breath sample by blowing directly into a disposable (single use) mouthpiece attached to a hand-held breath acetone analyzer. This test is entirely non-invasive and no sample is retained. At St Mary's Hospital, an additional breath sample will be collected for analysis by PTR-MS. This sample is stored temporarily (typically <24hrs) on a Thermal Desorption (TD) tube and destroyed during the analysis process.
- iii. Blood samples: blood samples (15ml) will be collected at each study time point. Where possible blood sampling will be combined with routine blood tests in order to avoid the requirement for repeated needle sticks. It is recognized that blood sampling can lead to temporary discomfort and a bruise where the needle enters the vein. Patients will be counselled about these risks as part of the process of giving informed consent.
- iv. Resting energy expenditure measurement by indirect calorimetry: this is an entirely non-invasive technique, however patients will be counselled regarding the possibility of feeling discomfort when the sample mask is applied over their mouth and nose.

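### Does the protocol plan a coefficient of variation for the Ketonix device without providing for the repeat readings it needs?

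*Protocol*

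**What the plan says.** Section B of the protocol lists as secondary outcome iii: "Assessment of the repeatability and accuracy of point of care testing of breath acetone using the Ketonix device". Data analysis in section E supplies the statistic for the repeatability half: "The coefficient of variation will be determined for repeated measurements recorded using the Ketonix device". The accuracy half is a Bland-Altman comparison with PTR-MS at St Mary's only.

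The collection side is less detailed. Breath sample collection in section E says "Patients will be asked to exhale directly into this handheld device" and gives no number of exhalations. Blood sampling, in the same section, does set a limit: "At each study time point a single sample of venous blood (15ml) will be collected".

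Section F describes what patients are asked to do. Under Human Subject involvement and characteristics: "Patients will be asked to donate an exhaled breath sample and blood sample (15ml) at two study time points". Under Sources of Materials, item ii: "Patients will be asked to provide a breath sample by blowing directly into a disposable (single use) mouthpiece". The same item adds, for St Mary's, that "an additional breath sample will be collected for analysis by PTR-MS".

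The Sample size text in section E also divides responsibilities: "Aspects of recruitment, consenting, data collection, and data storage will be the responsibility of each of the recruiting center".

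**The concern.** A coefficient of variation for device repeatability needs at least two readings taken close together under the same conditions. The analysis text assumes such readings exist, but no collection text states their number or spacing. The singular wording in section F can be taken to mean one breath per visit, and the only extra breath described goes to another instrument.

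If a site did record one Ketonix reading per visit, the loss could not be repaired, because an analysis plan cannot create readings that were never taken. The only repeats left would be staging and resection. Their difference contains the longitudinal change in acetone that is the primary outcome, so it does not measure device error. As each center is responsible for its own data collection, one could also worry that the two sites would proceed differently.

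**Working it through.** **Step 1. The text, side by side.**

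| Place in the protocol | What it says about the number of Ketonix readings |
|---|---|
| Section B, secondary outcome iii | Repeatability is to be assessed, so more than one reading is needed |
| Section E, Data analysis | Repeated Ketonix measurements are recorded and feed a CV |
| Section E, Breath sample collection | No number given |
| Section E, Blood sampling | A limit of one sample is stated, for blood only |
| Section F, Human Subject involvement | Breath sample in the singular, for patients of both sites |
| Section F, Sources of Materials, ii | Breath sample in the singular, plus an additional one for PTR-MS at St Mary's |

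Two entries require repeats, one is silent, one concerns blood, and two use the singular in a description of patient burden and risk.

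**Step 2. Can the singular be a count?** The Human Subject involvement text covers all 20 + 15 = 35 patients. Under Sources of Materials, the 15 patients at St Mary's give one breath to the Ketonix device and another for PTR-MS, so at least 1 + 1 = 2 breaths. Taken as a tally, the singular would be wrong for 15 of 35 patients. It is better read as naming the kind of material donated. This does not prove that replicates are taken, but it removes the main support for reading the text as one breath per visit. When the authors wanted a limit of one, as for blood, they wrote it.

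**Step 3. What the number of readings means for the estimate.** The protocol states no precision or replicate count, so there is no figure to reproduce. Inputs: 35 patients and two time points (section E), full attendance assumed, and m readings per visit, assumed to be 1, 2 or 3.

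- Patient-visits = 35 × 2 = 70.
- Within-visit df = visits × (m − 1).
- 95% confidence factors for the within-visit SD = √(df/χ²₀.₉₇₅) to √(df/χ²₀.₀₂₅), with roughly normal error on the analysis scale.

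| Visits with readings | m | df | 95% factors for the SD |
|---|---|---|---|
| 70 | 1 | 0 | not estimable |
| 70 | 2 | 70 × 1 = 70 | 0.858 to 1.198 |
| 70 | 3 | 70 × 2 = 140 | 0.895 to 1.133 |
| 35 (one visit per patient) | 2 | 35 × 1 = 35 | 0.811 to 1.304 |

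The factors apply approximately to the CV as well. Any reading of the plan that honors the CV sentence (m of 2 or more) gives a usable pilot estimate, even with replicates at only one visit per patient. Only m = 1 fails, and m = 1 conflicts with the Data analysis sentence.

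**Step 4. The cross-visit CV.** One could calculate how large a CV across staging and resection would be for an error-free device. The protocol does not plan that analysis, so such a figure would not measure a fault in it.

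**The case for a change.** The best case for a change is that the number of exhalations is a collection instruction, so it cannot be left to an analysis plan. The protocol gives this kind of detail elsewhere: one 15 ml blood sample, and about 5 minutes of calorimetry after 20 minutes seated. It gives none for the one device whose repeatability is an outcome. Validation of point of care acetone testing is a stated long-term aim, and the pilot is meant to inform later power calculations, so within-session error is of real interest. One sentence and a few extra non-invasive blows would settle it.

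Part of this stands. The number and spacing of readings are not written, and missing readings cannot be recovered later. A clarifying sentence would be harmless.

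The rest does not carry. Following the collection text literally does not produce one reading, because that text gives no number. To stop at one, a site would have to disregard both outcome iii and the CV sentence. Making each center responsible for its data collection does not hand it the choice of how many measurements to take, so divergence between sites is conjecture. Which value enters the primary outcome when replicates exist, the first or the mean, is commonly settled in the statistical analysis plan, which is not at hand.

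**Conclusion.** The concern does not call for a change. The protocol says that repeated Ketonix readings are recorded and what will be done with them. It leaves out how many and how far apart, an operational detail that staff working to outcome iii would fill sensibly. No passage contradicts the plan to take repeats.

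The reach is small: the repeatability half of one of three secondary outcomes, in a pilot of 35 patients. The primary outcome and the Bland-Altman comparison can be carried out either way. With duplicates at all 70 patient-visits the within-visit SD would be known to within about 0.86 to 1.20 times its estimate, assuming full attendance and roughly normal error.

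The conclusion rests on taking the Data analysis sentence at its word. It would change if it emerged that a site records only one Ketonix reading per visit, since within-visit repeatability could then not be estimated from that site.
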